7.2. Discussion of Design and Control

The study will enroll patients with MCI due to AD, mild AD, or moderate AD with amyloid deposition confirmed by amyloid PET imaging using NIAAA work group consensus guidelines (Albert et al. 2011; McKhann et al. 2011). The broad study population is justified for this study because amyloid pathology is well established before the diagnosis of MCI due to AD and does not differentiate during the later stages of disease. Thus, patients within this spectrum are essentially uniform for the purpose of testing LY3002813 effects on target engagement (Jack et al. 2010). Safety, PK, and PD were assessed in this study population in Study AACC for doses of up to 10 mg/kg. Japanese patients are included in this study to help enable the inclusion of Japanese patients in potential subsequent phases of development.

The single-dose arms in Part A are intended to be used to assess whether target engagement can be achieved after a single dose of 10 mg/kg LY3002813 or greater, given that there was evidence of a robust PD signal after only 3 doses of 10 mg/kg LY3002813. The multiple-dose arms will be used to assess a dose response and a time course of amyloid reduction based on florbetapir scans at baseline and at 12- to 24-week intervals. Twenty-four weeks of dosing in Part B is proposed to approximate the maximum duration of dosing leading to amyloid reduction in Study AACC; amyloid scans at 12 weeks and 24 weeks will be used to assess the time course of amyloid removal and identify whether shorter treatment duration (12 weeks) is sufficient. Sustainability of amyloid reduction after completion of 24 weeks of dosing will be assessed by florbetapir PET at 36, 48, and 72 weeks. The higher dose and more frequent dosing (Q2W) may reduce the incidence of immunogenicity identified in Study AACC. If a 12- or 24-week dosing duration is sufficient for amyloid removal, then the risks of immunogenicity and infusion reactions will potentially be limited to that treatment period. Chronic high-dose treatment (Q4W for up to 72 weeks) in Part C will assess the time course of the maximal PD effect and the opportunity to treat until maximum amyloid removal.

Multiple doses of 10 mg/kg IV were safe and tolerated in Study AACC. Although infusion reactions were observed in 6 out of 51 patients dosed with LY3002813, there were no infusion reactions in the 10 mg/kg dose cohort, despite the presence of ADAs. Clinical dosing of single dose of 20 mg/kg or multiple dosing of 10 mg/kg in Study AACD will only be initiated after safety review of the single 10-mg/kg dose of LY3002813.

MRI safety monitoring will occur 4 weeks after the first dose, every 12 weeks from the first dose, and up to 12 weeks after the last dose, with acquisition of sequences appropriate for

detecting vasogenic edema and microhemorrhage. These MRIs and MRIs at additional time points (ie, at 24 weeks, 48 weeks, and 72 weeks) will also provide volumetric and other imaging biomarker assessments. Microhemorrhages are believed to indicate a higher risk for macrohemorrhage as well as for the presence of significant amyloid angiopathy, and there appears to be a risk of microhemorrhage with antiamyloid treatment in preclinical models and in humans (eg, bapineuzumab, gantenerumab, aducanumab [Black et al. 2010]) as well. Although there was no evidence of ARIA-E by MRI at up to 10 mg/kg LY3002813 in Study AACC, this study will continue to monitor ARIA-E (and ARIA-H). The screening MRI scan will be used to exclude patients with >4 microhemorrhages. The 12-week interval between MRI scans is considered appropriate given the lack of ARIA-E observed up to 10 mg/kg LY3002813 in Study AACC.

8. Study Population

8.1. Criteria for Enrollment

Eligibility of patients for study enrollment will be based on the results of a screening medical history, physical and cognitive examination, clinical imaging tests, and the research disease diagnostic criteria ([Attachment 1](#)). The nature of any conditions present at the time of the physical examination and any preexisting conditions will be documented at screening.

Screening tests may occur up to 56 days before study drug administration except for the following:

Exceptions to the 56-day screening window: the maximum interval of time allowed from performance of screening tests to dosing is presented below. If the interval is greater than what is allowed, then that test may be repeated to meet enrollment criteria before dosing. Note that stable medical therapy for 2 months is a requirement before dosing regardless of the time elapsed for screening criteria.

- 1) MRI: 70 days
- 2) Free and Cued Selective Reminding Test with Immediate Recall (FCSRT-IR), Mini-Mental State Examination (MMSE), and Clinical Dementia Rating (CDR): 90 days
- 3) Florbetapir imaging enrollment: 160 days

Note that patients recruited at the Japan sites must be Japanese. Up to third-generation Japanese patients recruited at sites outside Japan can be counted as Japanese patients. To be considered as Japanese per protocol, patients outside of Japan should be up to third-generation Japanese, which is defined as all of the patient's biological grandparents are of exclusive Japanese descent and were born in Japan.

Individuals who do not meet the criteria for participation in this study may be re-screened. Individuals may be re-screened up to 1 time upon sponsor review. The interval between re-screenings should be at least 1 week. Each time re-screening is performed, the individual must sign a new informed consent form (ICF) and is assigned a new identification number.

Prospective approval of protocol deviations to recruitment and enrollment criteria, also known as protocol waivers or exemptions, are not permitted.

8.1.1. Inclusion Criteria

Patients are eligible for enrollment in the study only if they meet all of the following criteria:

- [1] Patients must meet all the research disease diagnostic criteria for MCI due to AD or mild to moderate AD below, consistent with NIAAA research diagnostic guidelines (Albert et al. 2011; McKhann et al. 2011):
 - a) gradual and progressive change in memory function reported by patients or informants over more than 6 months

- b) objective evidence of significantly impaired episodic memory characteristic of hippocampal dysfunction on testing: FCSRT-IR: <27 for free recall
(The episodic memory impairment can be isolated or associated with other cognitive changes at the onset or as the disease advances.) (Auriacombe et al. 2010; Grober et al. 2010)
- c) CDR = 0.5 to 2 and memory box score ≥ 0.5
- d) MMSE score 16 to 30
- e) positive florbetapir scan (central read)

[2] men or nonfertile women, at least 50 years of age. Nonfertile is defined as hysterectomy and/or bilateral oophorectomy, or amenorrhea for at least 1 year.

[3] have up to 2 reliable study partners, who will each provide written informed consent to participate, who are in frequent contact with the patient (defined as at least 10 hours per week) and 1 of whom at any 1 occasion will accompany the patient to the study visits, or will be available by telephone at designated times. If a patient has more than 1 study partner, it is preferred that 1 of them will be primarily responsible for the CDR and ADCS-MCI-ADL assessments.

The study partner(s) is/are required to accompany the patient for signing consent, on all dosing days and for all days that the Columbia Suicide Severity Rating Scale (C-SSRS)/Self-Harm Supplement Form and cognitive and functional scales are administered. If the study partner(s) is/are not able to accompany the patient in person because of an unavoidable circumstance, they must be available by telephone for the following assessments:

- AEs and concomitant medications
- relevant portions of the C-SSRS/Self-Harm Supplement Forms
- CDR and ADCS-MCI-ADL (primary study partner if possible)

If any study partner familiar with the study cannot continue, 1 replacement for each study partner is allowed, or more at the investigator's discretion. The replacement(s) will also need to sign a separate informed consent on the first visit that he/she accompanies the patient to participate.

Study partners must be able to communicate with site personnel and be willing to comply with protocol requirements, and in the investigator's opinion must have adequate literacy to complete the protocol-specified questionnaires.

[4] have adequate premorbid literacy, vision, and hearing for neuropsychological testing in the opinion of the investigator

[5] have given written informed consent approved by Lilly and the ethical review board (ERB) governing the site

- [6] are reliable and willing to make themselves available for the duration of the study and are willing to follow study procedures

8.1.2. Exclusion Criteria

Patients will be excluded from study enrollment if they meet any of the following criteria:

- [7] are investigator site personnel directly affiliated with this study and/or their immediate families. Immediate family is defined as a spouse, parent, child, or sibling, whether biological or legally adopted.
- [8] are Lilly employees or employees of third-party organizations (TPOs) involved with the study
- [9] have participated, within the last 30 days (for sites in Japan, 4 months) of screening, in a clinical trial involving an investigational product (other than the investigational product used in this study). If the previous investigational product has a long half-life, 3 months (for sites in Japan, 4 months) or 5 half-lives (whichever is longer) should have passed.
- [10] are persons who have previously completed or withdrawn from this study. This exclusion criterion does not apply to patients who are allowed to re-screen before randomization.
- [11] are persons who have previously participated in a study investigating LY3002813 and received active treatment with LY3002813
- [12] are persons who have previously participated in a study with active and/or passive immunization against A β (not including LY3002813)
- [13] have had gamma globulin therapy within the last 6 months
- [14] have allergies to either humanized monoclonal antibodies, diphenhydramine, epinephrine, or methylprednisolone
- [15] have a history of clinically significant multiple or severe drug allergies or severe post-treatment hypersensitivity reactions (including but not limited to erythema multiforme major, linear immunoglobulin A dermatosis, toxic epidermal necrolysis, and/or exfoliative dermatitis)
- [16] have known allergies to LY3002813, related compounds, or any components of the formulation; or history of significant atopy
- [17] have a clinically significant abnormality in the 12-lead ECG, including left bundle branch block, second or third degree heart block, or Bazett's corrected QT interval ≥ 470 msec for male patients or ≥ 480 msec for female patients, or intend to use drugs known to significantly prolong the QT interval within 14 days or 5 half-lives, whichever is longer, of a scheduled 18F-AV-1451 PET scan, or have a medical history of a risk factor of torsades de pointes
- [18] have an unacceptable blood pressure or pulse rate, as determined by the investigator (Note: patients may be on a stable hypertension medication)

- [19] show evidence of suicidal ideation within the last 6 months as assessed by the C-SSRS
- [20] show evidence of clinically significant active neuropsychiatric disease, deemed to be a risk to patient participation in the study, in the opinion of the investigator
- [21] show evidence of human immunodeficiency virus (HIV) infection and/or positive human HIV antibodies
- [22] Exclusion Criterion [22] has been deleted
- [23] are women who are lactating
- [24] have used stable medical therapy for less than 2 months for any concurrent medical condition that is not exclusionary
- [25] have donated blood of more than 500 mL within the last 30 days before dosing. For patients in Japan: have donated blood \geq 400 mL in the last 3 months (male patients) or in the last 4 months (female patients), or any blood donation (including apheresis) within the last 1 month, or total volume of blood donation within 12 months is 1200 mL (male patients) or 800 mL (female patients) at screening
- [26] have an average weekly alcohol intake that exceeds 21 units per week (male patients up to age 65) and 14 units per week (male patients over 65 and female patients), or are unwilling to stop alcohol consumption 48 hours before dosing until each discharge from the site (1 unit = 12 oz or 360 mL of beer; 5 oz or 150 mL of wine; 1.5 oz or 45 mL of distilled spirits)
- [27] have a known history of alcohol or drug abuse (as defined by the *Diagnostic and Statistical Manual, Fourth Edition, Text Revision* [APA 2000]) within 2 years of enrolling or a positive result regarding use of illicit drugs on the drug screening test
- [28] have current serious or unstable illnesses including hepatic disease (cirrhosis, hepatitis A, B, or C [presence of antibody to hepatitis B surface antigen in the setting of hepatitis B immunization is not an exclusion; the presence of hepatitis C antibody a normal liver function tests and a negative hepatitis C polymerase chain reaction is also not an exclusion]); renal, gastroenterologic, respiratory, cardiovascular disease (active ischemic heart disease [stable or unstable angina], intermittent atrial fibrillation); endocrinologic disease (stable non-insulin-dependent diabetes or stable thyroid disease is not an exclusion); neurologic disease (other than AD); psychiatric disease (including suicidal ideation); immunologic, infectious (HIV, tuberculosis, Lyme, or hematologic disease (including transfusion within past year), or other conditions that, in the investigator's opinion, could interfere with the analyses of safety in this study.
- [29] have a history of uncontrolled asthma, significant autoimmune disease (rheumatoid arthritis, systematic lupus erythematosus), hereditary angioedema, or common variable immune deficiency

- [30] have any contraindications for MRI, including claustrophobia or the presence of contraindicated metal (ferromagnetic) implants/cardiac pacemaker
- [31] have a head MRI (central read) demonstrating either greater than 4 cerebral microhemorrhages on T₂*-weighted gradient-echo sequence (regardless of their anatomical location), or a single area of superficial siderosis, or prior evidence of macrohemorrhage, or any other major intracranial pathology except: atrophy, meningiomas without mass effect, benign pituitary microadenomas, and/or mild to moderate white matter hyperintensities on fluid attenuation inversion recovery (FLAIR)
- [32] have a history of intracranial hemorrhage; cerebrovascular aneurysm or arteriovenous malformation; or carotid artery occlusion, stroke, or epilepsy

Exclusion criteria [33] to [36] only apply to patients who will require an LP during the study:

- [33] have criteria that would preclude an LP, such as allergy to all local anesthetics (such as lidocaine); have a local infection at the site of the LP; have ≤100 GI/L (100,000/mm³) platelets, clinically significant coagulation abnormality, or significant active bleeding; treatment with an anticoagulant or treatment with 2 or more antiplatelet agents or other drugs that affect coagulation or platelet function within 14 days before lumbar puncture
- [34] show clinically significant abnormalities in lumbar spine previously known or determined by screening lumbar x-ray or fluoroscopy (if conducted) that are considered incompatible with LP by the investigator and/or the person conducting the LP (if not the investigator)
- [35] in the opinion of the investigator have a history of clinically significant back pain, back pathology, and/or back injury (for example, degenerative disease, spinal deformity, or spinal surgery) that may predispose to complications or technical difficulty with LP
- [36] have medical or surgical conditions in which LP is contraindicated

Exclusion criteria [37] to [41] apply to all patients:

- [37] have poor venous access that would preclude IV drug delivery or multiple blood draws
- [38] have screening clinical laboratory test results with unacceptable deviations that are judged to be clinically significant by the investigator
- [39] have a history within the past 5 years of a primary or recurrent malignant disease with the exception of resected cutaneous squamous cell carcinoma in situ, basal cell carcinoma, cervical carcinoma in situ, or in situ prostate cancer with a normal prostate-specific antigen after resection

- [40] are being monitored for radiation due to occupational exposure to ionizing radiation, or exposure to ionizing radiation within last 12 months from an investigational study
- [41] in the opinion of the investigator or sponsor, are unsuitable for inclusion in the study

8.1.3. *Rationale for Exclusion of Certain Study Candidates*

Criteria [7] and [8] prevent conflict of interest in study participants. Criteria [9] through [41] exclude medical conditions, medication intolerance, and concomitant medication use that may constitute a risk for the patient and/or may confound the assessment of study endpoints.

8.2. Discontinuation

The reason for, and date of, discontinuation will be collected for all patients. All randomized patients who discontinue, regardless of whether or not they received investigational product, will have procedures performed as shown in the Study Schedule ([Attachment 1](#)).

8.2.1. *Discontinuation of Patients*

8.2.1.1. *Patients Inadvertently Enrolled*

The criteria for enrollment must be followed explicitly. If the investigator site identifies a patient who did not meet enrollment criteria and who was inadvertently enrolled, the sponsor must be notified. If the sponsor identifies a patient who did not meet enrollment criteria and who was inadvertently enrolled, the investigator site will be notified. A discussion must occur between the Lilly clinical pharmacologist or clinical research physician (CRP) and the investigator to determine whether the patient may continue in the study, with or without investigational product. Inadvertently enrolled patients may be maintained in the study and on investigational product when the investigator and Lilly clinical pharmacologist or CRP agree it is medically appropriate for that patient. The patient may not continue in the study with or without investigational product if the Lilly clinical pharmacologist or CRP does not agree with the investigator's determination it is medically appropriate for the patient to continue. The investigator must obtain documented approval from Lilly clinical pharmacologist or CRP to allow the inadvertently enrolled patient to continue in the study with or without investigational product.

8.2.1.2. *Discontinuations from Investigational Product or from the Study*

Patients will be discontinued from the investigational product and/or from the study in the following circumstances:

- enrollment in any other clinical trial involving an investigational product or enrollment in any other type of medical research judged not to be scientifically or medically compatible with this study
- investigator decision
 - the investigator decides that the patient should be discontinued from the study

- if the patient, for any reason, requires treatment with another therapeutic agent that has been demonstrated to be effective for treatment of the study indication, discontinuation from the study occurs prior to introduction of the other agent
- patient or study partner decision
 - the patient requests to be discontinued from the study
- sponsor decision
 - Lilly stops the study or stops the patient's participation in the study for medical, safety, regulatory, or other reasons consistent with applicable laws, regulations, and good clinical practice (GCP)
- AE
 - if a clinically significant event (CSE) occurs, the investigational product is to be discontinued and appropriate measures taken. Lilly or its designee should be alerted immediately. A CSE will be defined as a moderate to severe AE, abnormal clinical sign, or clinical laboratory finding that may pose a risk to the well-being of the patient. Refer to Section 10.6.
 - a clinically significant systemic hypersensitivity reaction occurs following administration of the LY3002813 (for example, drug-related symptomatic bronchospasm, allergy-related edema/angioedema, or hypotension), that requires parenteral medication, does not respond to symptomatic medication, or results in clinical sequelae or an anaphylactic reaction
 - Appearance of clinically significant new cerebral ischemic or hemorrhagic events by MRI, as judged by the investigator and agreed by the clinical pharmacologist/CRP
 - Appearance of symptomatic or asymptomatic ARIA-E (also known as cerebral vasogenic edema)
 - Appearance of symptomatic ARIA-H, including superficial siderosis, or an asymptomatic increase in the number of cerebral microhemorrhages >4 over baseline

Where possible, subjects who discontinue the investigational product because of an AE will continue with safety, PK, PD, and other assessments as per protocol and as deemed appropriate by the investigator and the Lilly clinical pharmacologist/CRP.

8.2.1.3. Suspension or Termination of Dosing for Either Dose Escalation or within a Dose Cohort

Dosing within a cohort, or dose escalation to a higher dose cohort (Cohorts 3, 5, 7), may be suspended or terminated if any of the following scenarios occur within a given dose cohort as determined by the unblinded Lilly CRP or clinical pharmacologist:

- 1) ≥ 2 patients experience an SAE that is considered related to LY3002813 administration. This would include:
 - a) signs and/or symptoms consistent with meningoencephalitis
 - b) fixed-focal neurological deficit
- 2) ≥ 2 patients experience evidence of clinically significant new cerebral ischemic or hemorrhagic events by MRI, as judged by the investigator and agreed by the clinical pharmacologist/CRP
- 3) ≥ 2 patients experience asymptomatic or symptomatic ARIA-E
- 4) ≥ 2 patients experience symptomatic ARIA-H, including superficial siderosis, or an asymptomatic increase in the number of cerebral microhemorrhages >4 over baseline
- 5) ≥ 2 patients develop clinically significant acute infusion AEs considered related to LY3002813 during or within 6 hours of completing the infusion that do not resolve with a reduced infusion rate and/or supportive care
- 6) ≥ 2 patients experience similar CSEs considered related to LY3002813. A CSE will be defined as a moderate to severe AE, abnormal clinical sign, or clinical laboratory finding that may pose a risk to the well-being of the patient.
- 7) 50% or more patients at a dose level experience moderate or severe AEs that impair normal activities, but do not meet the CSE criteria, and are considered related to study treatment
- 8) If an SAE occurs during the infusion of the study drug, irrespective of causality, the drug is discontinued immediately. No redosing or completion of dosing is considered for that patient. If the infusion SAE is considered related to LY3002813, then the remaining cohort is not dosed.

It is important to note that when the above criteria are met, the dosing at the same and higher dose levels may be suspended or terminated, but any ongoing dose level that is below the dose that triggered the stopping rule may continue when considered appropriate by the sponsor.

Any cohort that has been suspended may be re-initiated at a later date if a review of all available safety data by the sponsor supports this action. The decision to re-initiate the cohort, together with the supporting safety data, will be documented and shared with the investigators, institutional review board, and regulatory agencies, as appropriate. If multiple dose levels are involved, the original dose-escalation plans will be adhered to.

In the event of an SAE that is related to the investigational product, other than precautionary inpatient observation, dosing may be suspended, for that cohort and/or higher cohorts.

Refer to the Study Schedule ([Attachment 1](#)) for data collected at the time of discontinuation and follow-up.

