7.1.3. Part A: Single Dose Cohorts (Cohorts 1 through 3)

Safety, PK, and PD will be assessed in Cohorts 1 through 3 after single doses of LY3002813 or placebo. The planned doses are 10, 20, and 40 mg/kg IV for Cohorts 1, 2, and 3, respectively; with 8 patients (6 LY3002813; 2 placebo) planned to be enrolled in each cohort. Dose escalation will only occur after the safety from the preceding cohort has been established in at least 4 patients receiving LY3002813 and 1 receiving placebo. Safety data will be collected at least 1 week after dosing for dose escalation to Cohort 2 and at least 4 weeks after dosing for dose escalation to Cohort 3. Enrollment in Cohorts 2 and 3 will only commence once enrollment into the preceding cohort has completed. Safety, PK, and PD will be assessed at regular intervals for approximately 72 weeks (in Cohorts 1 and 2) or 24 weeks (in Cohort 3) after starting the dosing with study drug ([Attachment 1](#)).

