7.1.4. Part B: 24-Week Q2W Multiple Dose Cohorts (Cohorts 4 through 5)

Safety, PK, and PD will be assessed in Cohorts 4 and 5, during and after multiple doses of LY3002813 or placebo have been administered Q2W for 24 weeks. The planned doses are 10 and 20 mg/kg IV with 12 patients (9 LY3002813; 3 placebo) planned to be enrolled in each cohort. Cohort 4 (10 mg/kg IV Q2W for 24 weeks) will be initiated after review of the safety (at least 1 week after dosing) and PK data (complete Day 29 visit) from at least 4 patients receiving LY3002813 and 1 receiving placebo in Cohort 1. Cohort 5 (20 mg/kg IV Q2W for 24 weeks) will only be initiated after review of the safety and PK data (at least 4 weeks after dosing) from Cohort 2 in at least 4 patients receiving LY3002813 and 1 receiving placebo, and after confirmation that at least 2 patients have been dosed safely with LY3002813 at least 3 times each in Cohort 4. Safety and PD will be assessed at regular intervals for approximately 48 weeks after completion of 24 weeks of dosing with LY3002813 ([Attachment 1](#)).

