8.2.3. Discontinuation of the Study

The study will be discontinued if Lilly judges it necessary for medical, safety, regulatory, or other reasons consistent with applicable laws, regulations, and GCP.

9. Treatment

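### Stopping rules 6 and 7 leave a gap between them: 5 of 9 treated patients with lesser related AEs meet rule 7, but 4 plus one non-serious clinically significant event meet neither rule

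*Protocol*

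**What the plan says.** Protocol 8.2.1.3 lists eight scenarios. Dosing in a cohort, or escalation, may be halted for a time or for good "if any of the following scenarios occur within a given dose cohort as determined by the unblinded Lilly CRP or clinical pharmacologist". Two of them concern general AEs.

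- Rule 6: two or more "patients experience similar CSEs considered related to LY3002813". A CSE is "defined as a moderate to severe AE, abnormal clinical sign, or clinical laboratory finding that may pose a risk" to the patient's well-being.
- Rule 7: half or more of those at a given dose "experience moderate or severe AEs that impair normal activities, but do not meet the CSE criteria, and are considered related to study treatment".

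The other rules cover related serious AEs (SAEs), new cerebral events on MRI, ARIA-E, ARIA-H, acute infusion AEs that do not resolve, and SAEs during infusion. Below the list, a separate sentence lets dosing be suspended in that cohort or higher ones after a single related SAE.

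For the individual patient, 8.2.1.2 says that "if a clinically significant event (CSE) occurs, the investigational product is to be discontinued and appropriate measures taken", and that the sponsor should be alerted immediately.

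Cohorts 4 and 5 are planned "with 12 patients (9 LY3002813; 3 placebo) planned to be enrolled in each cohort" (7.1.4), and Cohorts 6 and 7 have the same split (7.1.5). Cohorts 1 to 3 have 6 treated and 2 placebo each, and escalation follows once safety has been "established in at least 4 patients receiving LY3002813 and 1 receiving placebo" (7.1.3).

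**The concern.** A CSE covers the same severity range as a rule 7 event and adds an element of risk to the patient. When an activity-impairing AE is judged to carry that risk, it drops out of rule 7. Rule 6 picks it up only if a second patient has a similar CSE. No listed rule adds the two counts, and none acts on one non-serious CSE or on several that differ.

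The pre-stated trigger can therefore switch off as events get worse. It can also switch off because an event was classed cautiously. At stake is the prompt that these rules give at cohort and escalation reviews, which in a trial this small can turn on one patient.

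**Working it through.** The documents state no probability for these rules, so there is no figure of the plan's to reproduce beyond the 50% threshold. The check is a count, followed by an illustration under assumed rates.

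**Step 1: counting.** Inputs: 9 treated per multiple-dose cohort, 6 per single-dose cohort, 4 at the minimum review. Each affected patient has one qualifying related event, and the CSE falls under none of rules 1 to 5 or 8. Rule 7 needs half of n, rounded up.

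| Treated | Non-CSE patients that meet rule 7 | Same number affected, one a CSE | Rule 7 | Rule 6 |
|---|---|---|---|---|
| 9 | 5 (5/9 = 55.6%) | 4 + 1 | 4/9 = 44.4%, not met | one CSE, not met |
| 6 | 3 (3/6 = 50%) | 2 + 1 | 2/6 = 33.3%, not met | one CSE, not met |
| 4 | 2 (2/4 = 50%) | 1 + 1 | 1/4 = 25%, not met | one CSE, not met |

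Rule 7 speaks of patients at a dose level and does not say whether placebo patients or other cohorts at that dose are included. The reversal does not depend on this. With all 12 patients of a cohort the threshold is 6, so 5 + 1 fails. With the 24 patients treated at 10 mg/kg (6 + 9 + 9) it is 12, so 11 + 1 fails.

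**Step 2: how often.** These values are assumptions, not in the documents: p is the chance that a treated patient has a qualifying related event, q the share of those events that are CSEs, and K the number of equally likely CSE types (K = 1 means that any two CSEs count as similar). No CSE is an SAE, MRI finding or unresolved infusion AE. Let a patients have a non-CSE AE and c a CSE, multinomial with probabilities p(1−q), pq and 1−p. With n = 9:

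- rule 7 as written: a ≥ 5;
- rule 6 not met: all c CSEs differ, with probability K(K−1)…(K−c+1)/K^c;
- gap: a + c ≥ 5, a ≤ 4 and rule 6 not met.

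For K = 1 the gap is the single case a = 4, c = 1, with coefficient 9!/(4!·1!·4!) = 630. At q = 0.2:

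- p = 0.3: 630 × 0.24⁴ × 0.06 × 0.7⁴ = 0.030
- p = 0.5: 630 × 0.40⁴ × 0.10 × 0.5⁴ = 0.101
- p = 0.6: 630 × 0.48⁴ × 0.12 × 0.4⁴ = 0.103

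Summing the same terms for larger K gives the chance that 5 or more of 9 are affected and neither rule is met:

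| p | K = 1 | K = 5 | K = 10 |
|---|---|---|---|
| 0.3 | 0.030 | 0.049 | 0.053 |
| 0.5 | 0.101 | 0.191 | 0.211 |
| 0.6 | 0.103 | 0.221 | 0.249 |

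Over K = 1 to 10, a CSE share of 10% gives 2 to 3% at p = 0.3 and 8 to 13% at p = 0.6. A share of 30% gives 3 to 7% and 9 to 34%.

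In smaller groups the K = 1 value at p = 0.6, q = 0.2 is similar: 60 × 0.48² × 0.12 × 0.4³ = 0.106 for n = 6 (2 + 1), and 12 × 0.48 × 0.12 × 0.4² = 0.111 for n = 4 (1 + 1).

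**Step 3: effect of counting CSEs in rule 7** (n = 9, q = 0.2), as the chance that rule 6 or 7 is met:

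| p | K | As written | CSEs counted |
|---|---|---|---|
| 0.3 | 1 | 0.138 | 0.168 |
| 0.3 | 10 | 0.054 | 0.107 |
| 0.6 | 1 | 0.670 | 0.772 |
| 0.6 | 5 | 0.522 | 0.743 |
| 0.6 | 10 | 0.489 | 0.738 |

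**The case against.** The strongest reply is that the plan as a whole responds more firmly to a CSE than to a rule 7 event. A CSE obliges the site to stop product in that patient and to alert the sponsor at once; rule 7 events carry no such duty. One related SAE already permits suspension, and 10.6.2 defines an SAE broadly enough to include an event that the investigator considers significant for any other reason. Many CSEs could qualify, and two related SAEs meet rule 1 even if they differ. Section 9.4.1 also treats events as related unless there is clear evidence otherwise.

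Escalation does not hang on these triggers either. Sections 9.4 and 9.4.1 require agreement between investigator and sponsor, and Cohort 3 enrolls only after Cohort 2 enrollment is complete, so 4 treated patients is a floor for the review. The sponsor's reviewer is unblinded, safety is evaluated every 3 months (10.6), and under 8.2.3: "The study will be discontinued if Lilly judges it necessary for medical, safety, regulatory, or other reasons".

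All of this stands, and it limits the consequence. It rules out three stronger readings that a reader might infer:

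- That a lone CSE goes unanswered. It does not; only the cohort-level count fails to register it.
- That all 9 of 9 patients could plausibly be affected with no trigger. The count allows it (4 non-CSE plus 5 CSEs), but only with five different related CSEs, none of them serious.
- That a patient taken off product is lost to rule 7. Under 8.2.1.2 such patients continue assessments where possible, so a later, separate non-CSE AE could still count.

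The size is also uncertain. The one clinical AE rate in the protocol is for a single event type: infusion reactions in 6 of 51 treated patients in the earlier study, with none at 10 mg/kg (7.2). The higher rates above are illustrations, not expectations.

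None of this removes the reversal for a related CSE that is not serious and falls under no other rule. Even if any two CSEs count as similar, the 4 + 1 case remains.

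**Conclusion.** The point holds in a limited form. For related CSEs that are not SAEs, MRI or ARIA findings, or unresolved infusion AEs, the written trigger moves the wrong way as severity rises: 5 of 9, 3 of 6 or 2 of 4 meet rule 7, while 4 + 1, 2 + 1 or 1 + 1 meet neither rule. This follows from the wording alone and needs no assumed rate, only that the CSE patient has no separate qualifying AE.

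How often it would matter does rest on assumptions: about 3 to 5% at a 30% event rate and 10 to 25% at 50 to 60%, with 9 treated, one fifth of events CSEs and none of them serious. If some CSEs were also SAEs, the chance that no listed ground for suspension applied would be smaller.

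A reader might infer that the sponsor could not stop, or that escalation would go ahead by default. The documents support neither, since the triggers are permissive and escalation needs agreement. This is a drafting fault in a safety rule and worth correcting in the next amendment.

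**What to change.** In rule 7, replace the exclusion of CSEs with their inclusion, so that it counts patients at a dose level who have either a moderate or severe AE that impairs normal activities or any CSE, in each case considered related to study treatment. Say any CSE, and not only AEs that meet the criteria, because a CSE may also be an abnormal sign or a laboratory finding. Leave rule 6 unchanged as the earlier trigger for two similar CSEs.

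An event reclassified from non-CSE to CSE then stays in the count, and 4 + 1 of 9 gives 5/9 = 55.6%, which meets the rule. Several differing CSEs that affect fewer than half the patients would still meet neither rule; the change does not claim to cover them.

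The cost is one line of protocol text, with no added patients, visits or staff. The trigger is met slightly more often: at a 30% event rate with 20% CSEs, 17% instead of 14% if any two CSEs are similar, or 11% instead of 5% with ten types. Each time, it only permits suspension or termination.
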